## Quantification of Tumor and Organ at Risk (OAR) Volume and Motion Path Changes during Definitive Photon or Proton Beam Radiotherapy

respiratory motion when calculating appropriate target volume margins. The distal esophagus can move 0.8cm radially and 1.8cm axially (Yaremko) and the pancreas can move 2.4 +/- 1.6 cm axially (Bussels). Lung tumors are significantly affected by respiratory motion and move 5-10 mm during quiet breathing and as much as 4.5 cm (Stevens) with deeper breaths. Therefore, accounting for respiratory motion can be extremely important for targeted radiation therapy.

The course of radiation treatment often lasts longer than 8 weeks. For patients with head and neck and gastrointestinal cancers, maintaining adequate nutrition during this time can be challenging. Studies have shown that about 35% of patients with head and neck cancers experience >10% weight loss and patients with gastrointestinal cancers experience weight loss ranging from 0-12% (Milano, Talamonti, Lin). Significant weight loss results in changes in patient anatomy, which can distort radiation dose distribution and therefore treatment efficacy.

In addition to patient anatomy the size of the tumor as well as the anatomic location of the tumor are subject to change during radiation treatment. Fox et al. demonstrated a median GTV reduction of 44.3% at 50Gy in patients with non-small cell lung cancer. Head and neck cancers and cervical cancers are particularly sensitive to radiation effects. Barker et al. demonstrated a 69.5% reduction in GTV volume with a median mass displacement of 3.3mm at the end of radiation treatment in patients with head and neck cancers. Cervical cancers have a median mid treatment regression rate of 69% at 36-45Gy when treated with radiation alone and 79% when treated with concurrent chemoradiation (Nam). The resulting anatomic changes during radiation treatment can have a significant impact on dosimetric distributions, resulting in inadequate dose delivery to the tumor even with 4D CT image guided radiotherapy planning (Britton). Britton et al. evaluated the dosimetric consequences of anatomic changes during conformal photon beam radiotherapy for 10 patients with NSCLC using weekly 4D CT Scans. The authors noted a substantial decrease (-20.5%) in the PTV dose coverage and variable increases in dose to normal tissue structures such as the lung, spinal cord, esophagus and heart. These variations were due to inter and intrafractional variations during treatment.

Ideally, one would account for both inter-and intrafraction variability on a daily basis or after a given number of fractions. (Vanuytsel, Vansteenkiste et al. 2000) This could widen the therapeutic ratio by maximizing dose to the tumor and protecting critical normal structures. Harsolia et al. found that in the treatment of patients with NSCLC, daily respiratory motion and tumor volume correction yielded the maximal decrease in treatment volumes (44% reduction) and the maximal decrease in volume normal lung irradiated (31% reduction) and mean lung dose (31% reduction).

At present, the standard of care is to base the entire course of radiation treatment upon the initial treatment plan, which is derived from the pre-treatment scan. It is easy to envision that treatment re-planning to adjust for anatomical changes may be necessary during the course of radiation treatment. The overall objective of this study is to determine the

**Quantification of Tumor and Organ at Risk (OAR) Volume and Motion Path Changes during Definitive Photon or Proton Beam Radiotherapy**

extent of tumor volume, tumor motion and patient anatomy variation during radiation treatment.

While tumor anatomic changes are important in radiation treatment with photon therapy, these factors are of particular concern when implementing proton therapy. Unlike photon beams, proton beams can deliver radiation that enters the body at low doses, but then uniformly delivers high doses of radiation to the tumor followed by a steep fall-off exit dose. These features allow high doses of radiation to be delivered to the primary tumor, with lower toxicity to normal tissue. Because of the sharp demarcations between low dose and high dose areas, proton therapy requires accurate delineation of the primary tumor in order to deliver adequate radiation dose to the tumor while limiting normal tissue toxicity. Therefore, adjusting for anatomic changes in tumors during radiation treatment is particularly important in proton therapy. Hui et al. studied the effect of anatomic changes on proton therapy dose distribution in lung cancer using weekly 4D CT Scans. Although only 8 patients were examined, there was variation in the CTV density as radiation treatment progressed. The authors concluded, however, that CTV coverage is adequate if tumor motion is taken into consideration with 4D CT planning. Interestingly, this CTV density variation was correlated with normal tissue toxicity, implying that as the tumor shrinks from radiation treatment, the high dose radiation spills over to normal tissue. The secondary objective of our study will be to utilize the serial imaging obtained from either the photon beam or proton beam patients to generate serial proton beam plans. This will allow us to estimate the dosimetric error with proton beam radiotherapy if tumor and patient anatomical changes are not accounted for during treatment.

We propose to quantify the changes in tumor volume, motion, and anatomic changes that occur during the time course of definitive radiotherapy in patients with lung cancers, head and neck cancers, gastrointestinal cancers (including but not limited to colorectal and rectal cancers) and gynecological cancers. These cancers were chosen as they represent the oncologic subsets that experience the greatest dynamic range in these variables during treatment.

### 3.0 SPECIFIC AIMS/OBJECTIVES

**Specific Aim 1:** To estimate the degree of tumor volume, tumor motion and patient anatomy change during treatment with photon beam radiotherapy.

- 1a. To estimate the degree and impact of tumor volume change during the course of definitive photon radiotherapy treatment in lung cancers, head and neck cancers, gastrointestinal cancers (including but not limited to colorectal and rectal cancers) and gynecological cancers.
- 1b. To estimate the degree and impact of tumor motion (anatomic location) change during the course of definitive photon radiotherapy treatment in lung cancers, head and neck cancers, gastrointestinal cancers (including but not limited to colorectal and rectal cancers and gynecological cancers).
- 1c. To estimate the degree and impact of changes in patient anatomy during the course of definitive photon radiotherapy treatment in head and neck and upper gastrointestinal cancers.

Hypothesis: Tumor volume and motion will change over the course of radiation treatment in patients with lung cancers, head and neck cancers, gastrointestinal cancers (including but not limited to colorectal and rectal cancers) and gynecological cancers. The weight loss experienced by patients with upper gastrointestinal and head and neck cancers will have a significant impact on their anatomy. These changes will alter the dose distribution of the photon beam treatment plans, possibly limiting radiation dose delivery to the target volumes and increasing radiation toxicity to surrounding critical structures.

**Specific Aim 2:** To estimate the error if tumor volume, tumor motion and patient anatomy change during treatment with proton beam radiotherapy.

- 2a. To generate simulated proton beam plans using serial CT or MR imaging obtained from either photon or proton beam patients to estimate the dosimetric error if these changes are unaccounted for during proton treatment.

[figure not shown]
Hypothesis: The changes in tumor volume and motion and patient anatomy will have a greater effect on appropriate dose distribution in plans using proton beam therapy compared to photon beam therapy given the need for more accurate target delineation in proton beam therapy.

### 4.0 STUDY OVERVIEW

This is a pilot study to estimate the degree of tumor volume, tumor motion and patient anatomy change during treatment with photon or proton beam radiotherapy. Patients will undergo simulation with an MR scan and/or CT scan per best clinical practices, and 4D

## Quantification of Tumor and Organ at Risk (OAR) Volume and Motion Path Changes during Definitive Photon or Proton Beam Radiotherapy

imaging will be employed as indicated, at the discretion of the treating radiation oncologist. Photon beam treatment plans and Proton beam treatment plans will be generated from these images. Based on the location of the primary tumor, patients will undergo either up to weekly 3D or 4D CT and/or serial MR scans during treatment. These images will be compared to the initial CT/MR scans used for treatment planning and analyzed for changes in tumor volume and tumor anatomic location. At the end of treatment, the frequent 3D or 4D CT and/or serial MR images will be compared to the initial treatment planning images to quantify the changes in tumor volume and tumor motion during the course of radiation treatment. Each CT and/or MR Scan will also be used to evaluate the changes in dose distribution to the target volumes and normal tissues that occur with the initial photon treatment plan and initial proton treatment. The changes in tumor volume, tumor motion and dose distribution during the course of radiation treatment will be analyzed to determine the effect of tumor changes on radiation treatment efficacy.

## 5.0 PARTICIPANT SELECTION

### 5.1 *Inclusion Criteria*

1. Patients aged  $\geq 18$
2. Biopsy proven diagnosis of non-small cell lung cancer, small cell lung cancer, head and neck, esophageal, gastric, pancreatic, hepatic, biliary, colorectal, anal, cervical, endometrial, vaginal, vulvar, ovarian cancer and any other gastrointestinal or gynecological cancers requiring definitive radiotherapy alone with or without concurrent chemotherapy.
3. Able to provide written informed consent and comply with all study procedures
4. Entire course of radiotherapy will be delivered at the University of Pennsylvania Perelman Center for Advanced Medicine.

### 5.2 *Exclusion Criteria*

1. Pregnancy or women of childbearing potential and men who are sexually active and not willing/able to use medically acceptable forms of contraception; this exclusion is necessary because the treatment involved in this study may be significantly teratogenic.

### 5.3 *Recruitment Procedures*

**Quantification of Tumor and Organ at Risk (OAR) Volume and Motion Path Changes during Definitive Photon or Proton Beam Radiotherapy**

Subjects will be recruited from the Oncology practices at Penn Medical Center. Patients will be referred by their physicians and include men and women who will be receiving radiotherapy with definitive intent with or without chemotherapy. Subjects will undergo an informed consent process in accordance with GCP. Informed consent will be obtained prior to the performance of any research specific (i.e. not standard of care) procedures and prior to the start of radiation therapy treatment. Subjects must meet all of the inclusion and none of the exclusion criteria as determined by baseline/eligibility measures. The treating radiation oncologist will approach and inform the patient about the study, thereby initiating the informed consent process. If the patient expresses interest in the study, the treating radiation oncologist will contact the Clinical Research Coordinator (CRC) in the Radiation Oncology department at the University of Pennsylvania and initiate introduction to the CRC. The treating radiation oncologist and/or CRC will interview the potential subject with privacy considerations, explain the requirements of the study and provide a copy of the Informed Consent Form. The treating radiation oncologist and/or CRC will state the volunteer nature of research and advise the subject to take sufficient time to discuss the study if necessary before making their decision to sign the informed consent document. If a decision to participate is made, the informed consent form is signed after which any research specific (i.e. not standard of care) procedures will be performed. Through use of the subject's electronic medical record and questions asked by the treating physician and/or CRC, patient eligibility based upon the inclusion/exclusion criteria will be verified. After the eligibility is established and confirmed with the treating physician/study investigator, a subject study number will be issued. All members of the research team will have successfully completed patient oriented research training. **Subjects will receive all treatment in the Radiation Oncology clinic of the University of Pennsylvania.**

## **6.0 STUDY PROCEDURES**

### ***6.1 Institutional and Investigator Requirements***

All patients must have a signed Informed Consent Form and a confirmation of eligibility form filled out and signed by a participating investigator prior to entering the study.

Confidential research charts will be kept in locked cabinet to which only members of the study team will have access. Subjects will be assigned a study number at the time of study enrollment. This study number and not the subject's name will be used on all case report forms.

#### **HIPAA Compliance:**

Patients will be asked to read and sign a combined study consent form and HIPAA consent form acknowledging the uses and disclosures of protected health information (PHI) in this study as required by The Health Insurance Portability and Accountability Act (HIPAA). PHI will not be shared with any outside institution except as required by law. Any reporting of the results of this study will be done only with de-identified patient data. Confidentiality will be protected as outlined below.

[figure not shown]
- Each subject will sign a combined study informed consent/ HIPAA authorization form prior to study entry.
- Each subject will be assigned a study number. All research-related material (to include specimens for research) will be labeled with the subject study number and the subject's initials.
- A list of the subject names with the associated subject numbers will be maintained by computer to which only members of the study team will have access.
- All research subject records will be kept in a study chart.
- An electronic database will be maintained. No subject names will be used in this database. Study numbers will be used. Only data which constitutes a limited data set (as defined by the University of Pennsylvania Health System in the HIPAA Privacy Education website) will be used.

#### ***6.1.1 Potential Risks to Patient***

Patients have additional radiation exposure with weekly 3D/ 4D CT and/or serial MR scans. The additional patient dose from a single CT scan is typically less than 10 cGy. This dose is less than 0.2% of a typical definitive treatment of 5,000cGy to 7,000cGy, and compares to the additive dose from portal images that have been used as standard of care in radiation oncology departments throughout the United States for decades. The added risk from additional radiation exposure due to these weekly scans therefore is minimal. There is no additional radiation risk from an MR scan.

Depending on specific diagnosis, the treating physician may elect to order the imaging (MR, CT, or MR/CT) with contrast. This involves giving intravenous gadolinium (for an MRI) or intravenous iodinated contrast (for a CT) before that specific scan to better visualize your tumor and internal anatomy. Gadolinium and iodine can pose a risk to people with kidney disease. This risk is not anticipated but this remains a possible risk that will require monitoring through blood drawn to measure kidney functions prior to each imaging scan during radiation treatment.

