**STUDY DESIGN**

- This is a pilot study to evaluate the changes in tumor volume, tumor motion, patient anatomy and dose distribution during the course of radiation treatment using up to weekly CT and/or MR Scans with the potential usage of contrast during the imaging procedure. We will analyze the effect of tumor changes and patient anatomy changes on radiation treatment efficacy.

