### **6.4. Study Calendar / Schedule**

Event	Baseline/Eligibility	Prior to RT Initiation	Weekly during RT
Informed Consent	X*	X*	
History and Physical	X	X	
Photon and Proton Treatment Planning and/or Baseline MR scan	X	X	
3D/4D CT and/or MR scans (determined by tumor location and treating physician)			X*
Blood Draw (prior to each imaging scan during RT)**		X	X

\* These are research specific procedures. All other procedures are standard of care.

\*\* Only if receiving contrast with imaging).

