## **Quantification of Tumor and Organ at Risk (OAR) Volume and Motion Path Changes during Definitive Photon or Proton Beam Radiotherapy**

expanded to create an internal tumor volume (ITV), which will include the GTV and the extent of GTV respiratory movement as defined by the 4D CT. The clinical tumor volume (CTV) and planning target volume (PTV) will be constructed from the GTV by an automatic margining tool supervised and edited by the treating radiation oncologist. The irradiation target volume will be defined by shaped ports with custom-made blocks or multileaf collimation. Portal verification shall be done for all treated fields. Megavoltage equipment is required with minimum peak photon energies of 6 MV. SAD techniques should be used. Each field will be treated every session. Interruptions in therapy should be discussed with the principal investigator but will be instituted at the discretion of the attending radiation oncologist.

Dose calculation should be performed using inhomogeneity corrections to account for differences in tissue density across the thorax. The total dose to gross disease will be 40-80 Gy, depending on the standard of care for using radiotherapy to treat the primary tumor (with or without concurrent chemotherapy) and on the site of the primary tumor. The prescribed total dose and dose per day will be constrained to adjust for the standard normal tissue dose limitations.

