### **6.6. *On Treatments***

Based on the primary tumor location and the discretion of the treating radiation oncologist, patients will undergo 3D/4D CT Scan (up to weekly) and/or MR Scan (minimum of 3).. The GTV, ITV and critical normal structures will be contoured on each up to weekly/serial scan. The up to weekly/serial GTV volume will be compared to the initial GTV volume to determine changes in tumor volume. Each GTV will be compared to the initial ITV volume to determine what percent of the GTV resides within the initial ITV. This value will be used to evaluate changes in tumor motion. Each ITV will be compared to the initial ITV. The initial photon treatment plan and proton treatment plan will be applied to the new scan. The amount of radiation dose to each GTV, ITV and critical normal structures will be recorded to determine the changes in dose distribution that occur as treatment progresses. **SUBJECTS WILL RECEIVE ALL SCANS IN THE RADIATION ONCOLOGY CLINIC OF THE UNIVERSITY OF PENNSYLVANIA.**

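### Contrast is elective, and its status is neither matched nor recorded across a patient's scans, so a contrast difference can pass as tumor volume change or CT dose change

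*Combined protocol and SAP*

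**What the plan says.** Contrast is optional throughout. The Study Design paragraph of the Protocol Overview describes imaging "with the potential usage of contrast during the imaging procedure". Section 6.1.1 says that, according to diagnosis, "the treating physician may elect to order the imaging (MR, CT, or MR/CT) with contrast", and that the agent is given "before that specific scan to better visualize your tumor and internal anatomy". The same section attaches "monitoring through blood drawn to measure kidney functions prior to each imaging scan during radiation treatment". The calendar in Section 6.4 marks that blood draw before radiotherapy and weekly during it, with the footnote "Only if receiving contrast with imaging".

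On-treatment imaging is chosen "Based on the primary tumor location and the discretion of the treating radiation oncologist" (Section 6.6). The main comparison follows in the same section: "The up to weekly/serial GTV volume will be compared to the initial GTV volume to determine changes in tumor volume". ITV is compared with its initial value in the same way, and the initial photon and proton plans are applied to every new scan.

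Section 6.5 (Radiation Treatment Planning) states: "Dose calculation should be performed using inhomogeneity corrections to account for differences in tissue density". That sentence goes on to refer to the thorax.

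Section 9.4 defines GTV as the primary tumor volume seen on the CT scan. Section 9.5 compares baseline with selected later scans by paired Wilcoxon signed-rank tests and fits random-effects models over time. Its item 6 looks for the first scan at which most patients in a stratum have important changes.

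**The concern.** The primary endpoint is a contoured volume, and a contour follows what can be seen. If one scan of a pair has contrast and the other does not, the contoured tumor can differ even though the patient has not changed. The within-patient design removes differences between patients. It does not remove a difference in acquisition between the two scans of a pair.

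The dose endpoint has a separate route, on CT only. A density-corrected calculation takes its input from the scan, so iodine present in one scan and absent in the other can change the recomputed dose without any anatomical change.

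The consequence is greatest for Section 9.5 item 6. True changes early in treatment are likely to be small. An artifact that is minor beside end-of-treatment shrinkage could still move the time point at which re-planning appears to be needed, and Section 9.2 says the study is meant to inform that decision.

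**Working it through.** **1. Does the text allow a mismatch, and would anything catch it?**

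- Choice: elective (6.1.1), potential (Study Design), conditional (6.4). No section requires follow-up contrast status to equal baseline status.
- Ordering context: Section 6.4 marks the on-treatment scans as research-specific and the planning scans as standard of care. The two stages are ordered for different reasons, so equal contrast use cannot be presumed.
- Measurement: 6.6 contours each scan and compares it with the initial volume. It names no contrast or non-contrast series for contouring or for dose calculation, and no density override.
- Data: contrast status is not among the items in 9.4.
- Analysis: 9.5 has no restriction to matched scans, no contrast term and no sensitivity analysis.

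A mismatch is therefore permitted, and no planned step would reveal it.

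**2. How large could the volume effect be?**

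The plan gives no figure for a contrast effect, so there is none to reproduce. Its only design number, 4 strata × 30 = 120, is consistent and plays no part here.

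Assumptions: a spherical tumor of radius r, with the visible edge shifted inward by d over the whole surface. Neither r nor d comes from the documents. Apparent volume loss = 1 − (1 − d/r)³.

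| r | d = 1 mm | d = 2 mm |
|---|---|---|
| 3.0 cm | 1 − 0.9667³ = 9.7% | 1 − 0.9333³ = 18.7% |
| 2.0 cm | 1 − 0.95³ = 14.3% | 1 − 0.90³ = 27.1% |
| 1.5 cm | 1 − 0.9333³ = 18.7% | 1 − 0.8667³ = 34.9% |

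The opposite switch would appear as growth of similar order. For example, a 1 mm outward shift at 2 cm gives 1.05³ − 1 = 15.8%.

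**3. Would the planned paired test pass it through?**

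As an illustration, 4,000 strata of 30 patients were simulated with no true volume change. The SD of the log volume ratio was 0.10 or 0.20. In a stated share of patients the mismatch made the later contour 5%, 10% or 20% smaller, always in the same direction. All of these inputs are assumptions. The two-sided signed-rank test at 0.05 rejected in:

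- about 5% of strata with no mismatch;
- 7% to 47% with mismatch in a quarter of patients;
- 10% to 96% with mismatch in half of patients.

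This shows only that a one-directional mismatch is not absorbed by pairing. It does not predict what will happen in this study.

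**4. Dose.** The documents give no basis for sizing the effect of iodine on recomputed dose, so no figure is offered. Section 6.5 states density correction with reference to the thorax. Applying the same reasoning to the other sites is an inference.

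**The case against.** The best defence is that contrast may be settled once per patient. The sentence in 6.1.1 ties the choice to diagnosis, which does not change between scans. The reference to a specific scan may describe only when the injection is given, and a blood draw both before and during radiotherapy fits contrast used throughout. This stands in part: the text permits mismatches but does not say they will occur. A reader might infer that contrast is decided scan by scan, and the documents do not establish that. The concern needs only that status may differ, and nothing prevents it.

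Second, the study is a descriptive pilot not powered for testing, so rejection rates carry little weight. That is fair, and the conclusion does not rest on them. Descriptive estimates of change are still biased by unlike scans.

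Third, images are archived (6.9, 7.0), so contrast status could probably be checked afterwards. That is plausible, but no such check is planned.

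Fourth, discarding unmatched pairs could remove scans non-randomly, and a matching baseline series may not exist. This stands and shapes the fix.

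Two further inferences are tempting. One is that contrast stops in patients whose kidney tests worsen, making the bias informative. Section 6.1.1 describes the kidney risk as not anticipated and gives no rule for withholding contrast. Section 6.8 withdraws patients with a contrast-related SAE, so they would not supply later mismatched scans. The other is that proton dose is affected most, which would tilt the photon-proton comparison. Section 2.0 attributes proton sensitivity to sharp dose gradients and target delineation, and no section links it to contrast.

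**Conclusion.** The concern holds as a gap in measurement control. The plan allows contrast status to differ between the scans it compares, does not record that status, and has no analysis that would separate a contrast difference from an anatomical one. It is a possible bias of undocumented frequency and size, not a demonstrated one.

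The volume figures of roughly 10% to 35% rest entirely on the assumed sphere, radius and 1 to 2 mm edge shift. They also apply GTV's CT-based definition to MR contours, as Section 6.6 implies. The dose effect applies to CT, is unsized, and is textually supported only for the thorax.

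A reader might set these figures against the 44.3% median lung reduction at 50 Gy cited in Section 2.0 and conclude that one switch equals a third or more of the whole effect. That does not hold in general: at 1 mm the ratio is 14.3/44.3 = 32% for a 2 cm radius and 9.7/44.3 = 22% for 3 cm. The head and neck (69.5%) and cervical (69% to 79%) reductions cited there are larger still. Contrast is unlikely to explain regressions of that size. It could distort small early changes and, through them, the time point sought in 9.5 item 6.

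**What to change.** Amend Sections 6.6, 9.4 and 9.5 as follows.

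- Record the contrast status of every scan, baseline included, on the case report form.
- Base the primary volume-change summary on pairs with the same modality and the same contrast status, using series already acquired.
- For CT dose recomputation, use a non-contrast series where one was acquired. Otherwise override contrast-enhanced voxels to their non-contrast density.
- Flag unmatched pairs, keep them, and report volume and dose results with and without them. Give the number of unmatched pairs at each time point.

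Who receives contrast stays a clinical decision, and no extra scan is required. The cost is one more form field, some contouring work for the overrides, and fewer pairs in the matched analysis. Reporting both sets of results guards against the matched subset being selective.
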